8.1.1 Non-serious adverse event(s)

The term AE is used to include both SAE and non-serious AE.

Non-serious AE are CTCAE grade ≤ 2 events or reactions listed in the the IB/SmPC of nivolumab. For FLOX, non-serious AE are CTCAE grade ≤ 2 events. Non-serious AE do *not* need to be *reported*. Also, AE or SAE that are definitely due to disease progression do *not* need to be *reported*; *c.f.*, Paragraph 8.3.

If an abnormal laboratory value or vital sign is associated with clinical signs and symptoms, the sign/symptom should be *reported as an AE* and the associated laboratory result/vital sign will be considered additional information to be collected on the relevant CRF.

The collection of non-serious AE information will begin at initiation of study drug and last until 100 days from the last dose of study drug (the 100-day injunction pertains to experimental arm patients only). Non-serious AE will be followed to resolution or stabilization, or *reported as SAE* if they become serious. Follow-up is also required for non-serious AE that cause interruption or discontinuation of study drug and for those present at the end of study treatment as appropriate. Identified non-serious AE will be *recorded* on a designated page of the CRF.

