8.1.2 SAE (serious adverse events)

An SAE is any untoward medical occurrence that at any dose:

- Results in death.
- Is immediately life-threatening.
- Requires in-patient hospitalization or prolongation of existing admission.
- Results in persistent or significant disability or incapacity.
- Is a congenital abnormality or birth defect.
- Is an important medical event that may jeopardize the subject or may require medical intervention to prevent one of the outcomes listed above. Examples of such events include but are not limited to intensive treatment in an emergency room or at home for allergic bronchospasm, blood dyscrasias, or convulsions that do not result in hospitalization. Potential drug-induced liver injury (DILI) is also considered an important medical event (see Paragraph 8.7 for the definition of potential DILI).

Suspected transmission of an infectious agent (*e.g.*, pathogenic or nonpathogenic) via the study drug is an SAE.

Although pregnancy, overdose, cancer, and potential DILI are not always serious by regulatory definition, these events must be handled as SAE (see Paragraph 8.5 for reporting pregnancies).

Any component of a study end point that is considered related to study therapy (e.g., death is an end point; if death occurred due to anaphylaxis, anaphylaxis must be reported) should be reported as SAE.

Note:

The following hospitalizations are not considered SAE in this study:

- A visit to the emergency room or other hospital department for <24 hours which does not result in admission (unless considered an important medical or life-threatening event).
- Elective surgery planned prior to signing consent.
- Admission for a planned medical/surgical procedure.
- Routine health assessment requiring admission for baseline/trending of health status (e.g., routine colonoscopy).
- Medical/surgical admission other than to remedy ill health and planned prior to entry into the study. Appropriate documentation is required in these cases.
- Admission encountered for another life circumstance that carries no bearing on health status and requires no medical/surgical intervention (e.g., lack of housing, economic inadequacy, caregiver respite, family circumstances, administrative reason).
- Admission for administration of anti-cancer therapy in the absence of any other SAE.

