8.9 AE (adverse events) recording

If the patient has experienced an AE, Clinical Investigator will record the following information in the CRF:

- The nature of the AE will be described in precise standard medical terminology (*i.e.*, not necessarily the exact words used by the patient).
- The duration of the event will be described in terms of event onset date and event ended date.
- The intensity of the AE will be defined according to CTCAE v4.0.
- The causal relationship of the event to the IMP will be assessed as one of the following:

Unrelated: There is no temporal relationship to IMP administration (too early or late, or IMP not administered), or there is a reasonable causal relationship between non-investigational product, concurrent disease, or circumstance and the AE.

Unlikely: There is a temporal relationship to IMP administration, but there is not a reasonable causal relationship between the IMP and AE.

Possible: There is reasonable causal relationship between the IMP and AE. Dechallenge information is lacking or unclear.

Probable: There is a reasonable causal relationship between the IMP and AE. The event responds to dechallenge. Rechallenge is not required.

Definite: There is a reasonable causal relationship between the IMP and AE.

- Action taken.
- The outcome of the AE – whether the event is resolved or still ongoing.

It is important to distinguish between serious and severe AE. Severity is a measure of intensity whereas seriousness is defined by the criteria in Paragraph 8.1.2. An AE of severe intensity needs not necessarily be considered serious. For example, nausea that persists for several hours may be considered severe nausea, but is not an SAE. On the other hand, a stroke that results in only a limited degree of disability may be considered a mild stroke, but would be an SAE.

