#### 5.2. Analysis methods

*Main statistical analyses.* The main statistical analysis is planned after the last patient has fulfilled the pre-defined follow-up period. PFS will be calculated from the day of randomization to first recorded disease progression according to RECIST v1.1 or when applicable iRECIST, or death. Patients who have not had disease progression at the time of final analysis will be censored at the date last known to be alive and progression-free. The analyses will compare the treatment groups in total as well as groups stratified by primary tumor sidedness and (K)RAS/BRAF mutation status.

*Interim analyses.* Interim analyses will apply to data on safety, tolerability, possible detrimental effects, and curative outcomes, and will be based on purely clinical judgment by the External Data and Safety Monitoring Committee. These types of data will be reported as the number of events.

*Descriptive statistics.* Demographic and clinical characteristics will be presented as means and standard deviations, medians with minimum and maximum values, or frequencies and percentages, as appropriate. Further statistical analyses will be separated to primary analyses, including only comparison of primary end point between two treatment arms, and secondary analyses, including stratified analyses on primary and secondary end points as well as number of analyses on secondary end points.

*Primary analysis.* Median PFS time will be compared between study arms by drawing Kaplan-Meier survival curves and performing log-rank test. HR with the corresponding 95% CI and p-values will be estimated by Cox proportional hazards model.

*Secondary analyses.* Distribution of PFS times stratified by the primary tumor sidedness and (K)RAS/BRAF mutation status will be illustrated graphically by Kaplan-Meier curves and compared by log-rank test. To assess the hazard rates for disease progression within each strata, Cox proportional hazards model will be estimated and, if appropriate, adjusted for relevant covariates. The results will be presented as HR with the corresponding 95% CI and p-values.

Safety. The number of serious adverse events (SAE) will be summarized and presented by trial arm. In addition, information will be given on the number of SAE per participant, together with details on the causality, expectedness, and outcome of each SAE experienced. Summaries of suspected unexpected serious adverse reaction (SUSAR) events will also be presented by trial arm.

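### Protocol 8.1.1 defines non-serious events by grade and, for nivolumab, by listing, which contradicts the outcome-based definition of seriousness in 8.1.2, 8.2 and 8.9

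*Protocol*

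**What the plan says.** Protocol 8.1.1 divides adverse events into serious and non-serious. It describes the second class twice, once per treatment. For nivolumab: "Non-serious AE are CTCAE grade ≤ 2 events or reactions listed in the the IB/SmPC of nivolumab". For chemotherapy, grade is the only test: "For FLOX, non-serious AE are CTCAE grade" 2 or lower. It then states that non-serious events need not be reported, although they are to be recorded on a CRF page, and that one which becomes serious is to be reported as an SAE.

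Protocol 8.1.2 defines an SAE by what happens to the patient. One criterion is "Requires in-patient hospitalization or prolongation of existing admission". It contains no grade, listing or drug test.

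Protocol 8.2 requires all SAEs in both arms to be collected, related or not, and sent to the sponsor within 24 hours. It asks for an SAE report whenever seriousness is in doubt. It gives the Investigator's Brochure and the SmPCs one role, which is to settle expectedness.

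Protocol 8.9 refers seriousness to 8.1.2 and warns that "An AE of severe intensity needs not necessarily be considered serious".

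SAP 5.2 plans the analysis: "The number of serious adverse events (SAE) will be summarized and presented by trial arm". It gives no definition of seriousness of its own.

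**The concern.** Severity, expectedness and seriousness are three separate properties of an event. Most of the safety chapter keeps them apart, but 8.1.1 uses the first two to decide the third, and it is also the section that says which events need not be reported. A site that reads 8.1.1 as its working rule could leave out an event that 8.1.2 calls serious.

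Two things depend on this. One is prompt reporting: the 24-hour rule in 8.2 applies only to an event that has been recognised as serious, and Protocol 4.6 says that no safety data yet exist for the sequential regimen. The other is the safety analysis: SAEs are tabulated by arm (Protocol 10.4.5, SAP 5.2), and safety is compared between arms by a χ² or Fisher's exact test. The listing clause concerns a drug given in one arm only, so any misclassification that it causes need not fall equally on the arms.

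**Working it through.** The plan states no figure on this point, and the documents give no SAE rate. The check is therefore a comparison of texts.

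**Step 1: how the nivolumab sentence can be read.** The phrase "events or reactions listed in the the IB/SmPC of nivolumab" follows a grade limit, and its grammar allows three readings:

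- Reading A: grade 2 or lower events, plus listed reactions of any grade. The exemption is wider for nivolumab than for FLOX.
- Reading B: grade 2 or lower events or reactions, and only if listed. The exemption is narrower for nivolumab than for FLOX.
- Reading C: the grade limit covers both nouns and the listing only the second. The listing then adds nothing, and the rule equals that for FLOX.

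**Step 2: the rules applied to the same events.**

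| Event | Under 8.1.1 | Under 8.1.2, 8.2 and 8.9 |
|---|---|---|
| FLOX event, grade 2, unplanned admission (either arm) | Non-serious, no report | SAE, 24-hour report |
| Listed nivolumab reaction, grade 2, unplanned admission | Non-serious on A, B and C | SAE, 24-hour report |
| Unlisted nivolumab event, grade 2, unplanned admission | Non-serious on A and C, not on B | SAE, 24-hour report |
| Listed nivolumab reaction, grade 3, unplanned admission | Non-serious on A, not on B or C | SAE, 24-hour report |
| FLOX nausea, severe, several hours, no 8.1.2 criterion met | Outside the non-serious class if grade 3 | Severe but not an SAE (the example in 8.9) |

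The first two rows conflict on every reading. The fourth conflicts only on A. The last row is a conflict in the other direction: with only two classes, a grade 3 FLOX event would be serious by default, which 8.9 rejects.

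**Step 3: whether the data could repair a misclassification.** Protocol 8.10.1 sends all AEs and SAEs to the CRF, which would allow reclassification later. SAP 5.5 limits safety recording to grades 3 to 5, with one grade 2 exception for immune-related hepatotoxicity. If that limit governs the data, a grade 2 event with admission, treated as non-serious, might not be recoverable.

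**Step 4: sensitivity, under assumptions only.** Suppose that the true proportion of patients with an SAE is p in both arms, with p assumed at 30% to 50%, that there are 50 patients per arm, and that a share m of SAE patients goes uncounted in one arm, whichever that is. The spurious difference is p × m. The last column is the normal-approximation probability that a two-sided 5% test of two proportions is significant in the direction of the loss.

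| m (assumed) | p × m | Probability |
|---|---|---|
| 0 | 0 | 2.5% (nominal) |
| 10% | 3 to 5 points | 5% to 7% |
| 25% | 7.5 to 12.5 points | 13% to 24% |
| 50% | 15 to 25 points | 43% to 74% |

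Nothing in the documents places m within this range. If sites follow 8.1.2 and 8.2, m is 0.

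**The case against.** The strongest reply is that one outcome-based SAE definition already covers every drug and both arms. Section 8.2 requires all SAEs to be collected in both arms, and 8.9 refers seriousness back to 8.1.2. Where the sections clash, the doubt rule in 8.2 should produce a report, and 8.1.1 itself upgrades an event that becomes serious. Other text also speaks against Reading A. Protocol 5.7.2.7 judges grade 3 and 4 nivolumab infusion reactions by the 8.1.2 criteria, 8.7 makes potential drug-induced liver injury an SAE, and the plan to report expectedness for each SAE would be empty for nivolumab if listed reactions could not be SAEs. Severe events would also stay visible in the by-arm tables of CTCAE grade.

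Much of this stands. It shows what the authors probably meant, and it rules out treating a distortion as established. It does not remove the conflict. The upgrade clause covers events that change, not events placed in the wrong class at the outset. The doubt rule helps only an investigator who is in doubt, and an explicit definition tends to remove doubt. The grade tables do not show whether a patient was admitted.

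A reader might go further and infer that the SAE counts are not comparable, with a lean towards fewer SAEs in the experimental arm, because the listing clause concerns nivolumab and control patients receive 8 FLOX cycles per sequence against 4. The documents do not support that. The lean needs Reading A, or grade 3 FLOX events counted as serious against 8.9. Reading B would point the other way for nivolumab, Reading C would add no difference between the drugs, and the grade limit for FLOX events applies in both arms.

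**Conclusion.** The contradiction is real and lies in the current text. Section 8.1.1 cannot be followed literally together with 8.1.2, 8.2 and 8.9. A grade 2 or lower FLOX event needing admission is labelled non-serious in either arm, and on one of three readings so is a listed nivolumab reaction of any grade.

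The consequence is conditional. If sites apply 8.1.1 ahead of 8.1.2, serious events may miss 24-hour reporting and SAE counts by arm may not be fully comparable. If they apply 8.1.2 and 8.2, nothing is distorted. Size and direction cannot be determined from the documents. The sensitivity table shows only how a comparison of 50 with 50 patients would react to an assumed loss in one arm, and it is not an estimate for this trial.

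**What to change.** In Protocol 8.1.1, define a non-serious AE, for both arms and all study drugs, as any AE that meets none of the 8.1.2 criteria. Remove the grade limit and the IB/SmPC listing from that definition. Keep CTCAE grade as the measure of severity and the IB/SmPC as the reference for expectedness, as 8.2 and 8.9 already do. In SAP 5.2, add one sentence stating that the SAE table uses the 8.1.2 definition.

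The cost is one amended protocol paragraph, one sentence in the SAP, an instruction to sites, and somewhat more SAE reports. The change concerns classification and reporting only and alters no treatment rule.

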8.1.2 SAE (serious adverse events)

An SAE is any untoward medical occurrence that at any dose:

- Results in death.
- Is immediately life-threatening.
- Requires in-patient hospitalization or prolongation of existing admission.
- Results in persistent or significant disability or incapacity.
- Is a congenital abnormality or birth defect.
- Is an important medical event that may jeopardize the subject or may require medical intervention to prevent one of the outcomes listed above. Examples of such events include but are not limited to intensive treatment in an emergency room or at home for allergic bronchospasm, blood dyscrasias, or convulsions that do not result in hospitalization. Potential drug-induced liver injury (DILI) is also considered an important medical event (see Paragraph 8.7 for the definition of potential DILI).

Suspected transmission of an infectious agent (*e.g.*, pathogenic or nonpathogenic) via the study drug is an SAE.

Although pregnancy, overdose, cancer, and potential DILI are not always serious by regulatory definition, these events must be handled as SAE (see Paragraph 8.5 for reporting pregnancies).

Any component of a study end point that is considered related to study therapy (e.g., death is an end point; if death occurred due to anaphylaxis, anaphylaxis must be reported) should be reported as SAE.

Note:

The following hospitalizations are not considered SAE in this study:

- A visit to the emergency room or other hospital department for <24 hours which does not result in admission (unless considered an important medical or life-threatening event).
- Elective surgery planned prior to signing consent.
- Admission for a planned medical/surgical procedure.
- Routine health assessment requiring admission for baseline/trending of health status (e.g., routine colonoscopy).
- Medical/surgical admission other than to remedy ill health and planned prior to entry into the study. Appropriate documentation is required in these cases.
- Admission encountered for another life circumstance that carries no bearing on health status and requires no medical/surgical intervention (e.g., lack of housing, economic inadequacy, caregiver respite, family circumstances, administrative reason).
- Admission for administration of anti-cancer therapy in the absence of any other SAE.

8.2 SAE (serious adverse events) collection and reporting

For nivolumab, the IB represents the reference safety information to determine expectedness of SAE for expedited reporting. For the FLOX regimen, the SmPC of each of the drug components represents the reference safety information. Following the subject's written consent to participate in the study, all SAE (in both study arms), whether related or not related to study drug, must be collected, including those thought to be associated with protocol-specified procedures. All SAE must be collected that occur during the screening period and within 100 days of the last dose of nivolumab. If applicable, SAE must be collected that relate to any later protocol-specified procedure.

Clinical Investigator must report any SAE that occurs after these time periods and that is believed to be related to any IMP or protocol-specified procedure, pertaining to the full duration of the study (c.f., Paragraph 7.8), which is in accordance with European Commission guidelines.

An SAE report must be completed for any event where doubt exists regarding its seriousness.

If Clinical Investigator believes that an SAE is not related to study drug, but is potentially related to the conditions of the study (such as withdrawal of previous therapy or a complication of a study procedure), the relationship must be specified in the narrative section of the SAE report form.

SAE, whether related or not related to study drug, and pregnancies, must be reported to Sponsor (or designee) within 24 hours of awareness of the event. SAE will be recorded on the Suspect Adverse Reaction Report form by the Council for International Organizations of Medical Sciences (CIOMS), c.f. Appendix 10. Pregnancies will be recorded on a Pregnancy Surveillance Form.

If only limited information is initially available, follow-up reports are required. All SAE must be followed to resolution or stabilization.

If an ongoing SAE changes in its intensity or relationship to study drug or if new information becomes available, the SAE report must be updated and submitted within 24 hours to Sponsor (or designee) using the same procedure used for transmitting the initial SAE report.

Sponsor's representative for SAE notifications has the following address:

[contact]

and

Cell Phone: ([contact]

Sponsor will immediately forward SAE notifications (in experimental arm patients) to the following address:

[contact]

or

Facsimile Number: (+1) [contact]

8.3 Disease progression or recurrence

Disease progression can be considered as a worsening of a patient's condition attributable to the disease for which the IMP is being studied. It may be an increase in the severity of the disease under study and/or increase in the symptoms of the disease. Expected progression of the disease under the study and/or expected progression of signs and symptoms of the disease under study, unless more severe in intensity or more frequent than expected for the patient's condition, will not be reported as AE. Events which are definitely due to disease progression will not be reported as AE. However, if Clinical Investigator considers that there was a causal relationship between treatment with IMP or protocol design/procedures and the disease progression/recurrence, this will be reported as SAE.

Death due to progressive disease will be recorded on a specific form in the CRF and not as SAE. Any new primary cancer (non-related to the cancer under study) will be considered for reporting as SAE.

8.4 Laboratory test abnormalities

The following laboratory test abnormalities will be captured on the non-serious AE CRF page or SAE report form as appropriate:

- Any laboratory test result that is clinically significant or meets the definition of SAE.
- Any laboratory test result abnormality that requires the subject to have study drug discontinued or unintendedly interrupted.
- Any laboratory test result abnormality that requires the subject to receive specific corrective therapy.

It is expected that wherever possible, the clinical rather than laboratory term would be used by the reporting investigator (e.g., anemia *versus* low hemoglobin value).

8.5 Pregnancy

If, following initiation of the study drug, it is subsequently discovered that a study subject is pregnant or may have been pregnant at the time of study exposure, including during at least 5 half-lives after administration of nivolumab, Clinical Investigator must immediately notify Sponsor of this event and complete and forward a Pregnancy Surveillance Form (provided upon request from BMS) to Sponsor and BMS (in the case of an experimental arm patient) within 24 hours of awareness of the event and in accordance with SAE reporting procedures.

In this case, the IMP will be permanently discontinued in an appropriate manner.

Follow-up information regarding the course of the pregnancy, including perinatal and neonatal outcome and, where applicable, offspring information must be reported on the Pregnancy Surveillance Form.

Any pregnancy that occurs in a female partner of a male study participant should be reported to Sponsor and BMS (in the case of an experimental arm patient). Information on this pregnancy will be collected on the Pregnancy Surveillance Form.

8.6 Overdose

An overdose is defined as the accidental or intentional administration of any dose of a product that is considered both excessive and medically important. All occurrences of overdose must be reported as SAE.

